9. STATISTICAL METHODS AND SAMPLE SIZE DETERMINATION

[figure not shown]
We will employ the Bayesian optimal interval (BOIN) design (Yuan et al., 2016) to find the MTD. The target toxicity rate for the MTD is $\phi = 0.25$ and the maximum sample size is 18. We will enroll and treat patients in cohorts of size 3. DLTs are defined in Section 6.2, and only those DLTs that occur within the first 6 weeks will be used for dose finding. To guide dose-escalation decisions, if the observed DLT rate at the current dose is ≤ 0.236 , the next cohort of patients will be treated at the next higher dose level; if it is ≥ 0.359 , the next cohort of patients will be treated at the next lower dose level. For the purpose of overdose control, doses j and higher levels will be eliminated from further examination if $\Pr(p_j > 0.25 |$

data) > 0.95 , where p_j is the true DLT rate of dose level j , $j = 1, 2, 3$. When the lowest dose is eliminated, stop the trial for safety. The trial design is illustrated in **Figure 3** and described as follows:

1. Patients in the first cohort are treated at dose level 1.
2. To assign a dose to the next cohort of patients, conduct dose escalation/de-escalation according to the rule displayed in **Table 12**, which minimizes the probability of incorrect dose assignment. When using **Table 12**, please note the following:
 - a. “Eliminate” means eliminate the current and higher doses from the trial to prevent treating any future patients at these doses because they are overly toxic.
 - b. When we eliminate a dose, automatically de-escalate the dose to the next lower level. When the lowest dose is eliminated, stop the trial for safety. In this case, no dose should be selected as the MTD.
 - c. If none of the actions (i.e., escalation, de-escalation or elimination) is triggered, treat the new patients at the current dose.
 - d. If the current dose is the lowest dose and the rule indicates dose de-escalation, treat the new patients at the lowest dose unless the number of DLTs reaches the elimination boundary, at which point terminate the trial for safety.
 - e. If the current dose is the highest dose and the rule indicates dose escalation, treat the new patients at the highest dose.
3. Repeat step 2 until the maximum of 5 evaluable patients are treated on the highest dose, or maximum sample size of 15 is reached or end enrollment when the number of patients treated at the current dose ≥ 9 and the decision based on **Table 12** is to stay at the current dose.

Table 12. Dose escalation/de-escalation rule for the BOPIN design

Actions	The number of patients treated at the current dose											
	1	2	3	4	5	6	7	8	9	10	11	12
Escalate if # of DLT \leq	0	0	0	0	0	1	1	1	1	1	2	2
De-escalate if # of DLT \geq	1	1	1	2	2	2	3	3	3	3	4	4
Eliminate if # of DLT \geq	NA	NA	3	3	3	4	4	4	5	5	6	6

$$* \text{DLT rate} = \frac{\text{Total number of patients who experienced DLT at the current dose}}{\text{Total number of patients treated at the current dose}}$$

Figure 3. Flowchart for trial conduct using the BOIN design

After the trial is completed, select the MTD based on isotonic regression as specified in Liu and Yuan (2015). This computation is implemented by the "Estimate MTD" tab of the BOIN Design Desktop Program (Venier et al., 2017). Specifically, select as the MTD the dose for which the isotonic estimate of the toxicity rate is closest to the target toxicity rate. If there are ties, select the higher dose level when the isotonic estimate is lower than the target toxicity rate and select the lower dose level when the isotonic estimate is greater than or equal to the target toxicity rate. In general, the MTD will be used as the R2PD for phase II part, but might be adjusted based on the PK/PD and total evidence.

Table 13 shows the operating characteristics of the trial design based on 1000 simulations of the trial using the BOIN Design Desktop Program (Venier et al., 2018). The operating characteristics show that the design selects the true MTD, if any, with high probability and allocates more patients to the dose levels with the DLT rate closest to the target of 0.25.

Table 13. Operating Characteristics of the BOPN design

	Dose Level			Number of Patients	% Early Stopping
	1	2	3		
Scenario 1					
True DLT Rate	0.25	0.42	0.59		
Selection %	73.4	19.1	1.2		6.3
# Pts Treated	8.2	3.0	0.6	11.75	
Scenario 2					
True DLT Rate	0.10	0.25	0.40		
Selection %	28.9	56.6	14.5		0.0
# Pts Treated	6.7	5.0	2.4	14.08	
Scenario 3					
True DLT Rate	0.05	0.12	0.25		
Selection %	6.0	40.0	54.0		0.0
# Pts Treated	4.8	5.1	4.9	14.75	

The trial will be completed after the RP2D is determined as described above. The section below is maintained in the protocol in order to reference the original design and will no longer apply.

After the RP2D is determined, subsequent patients will be randomized in a 3:1 manner for enrollment into the respective AVB-S6-500 and Durvalumab monotherapy arms. We estimate accrual rate of 3 patients per month. We anticipate a dropout rate of approximately 8-10% due to possible toxicity as seen in prior literature of checkpoint inhibitor therapy [61], [62], and subsequent inability to proceed to combination treatment. All patients who complete the monotherapy treatment phase will proceed to combination treatment, at which time receipt of at least one dose of combination therapy at the final determined dosing defines evaluable patients. As mentioned above, should the safety lead-in phase in the combination treatment require dose adjustment, only those patients who received the RP2D and completed one cycle of combination treatment will be considered evaluable for the primary outcome of response rate to combination therapy and used for making go/no-go decision as described below.

In terms of outcome assessment of response rate and toxicity to combination therapy, the Bayesian optimal phase 2 (BOP2) design is utilized to jointly monitor toxicity and efficacy [63]. The first 12 patients to receive combination treatment constitutes the first stage. Of these N=12 patients, if 1 or more responses are detected and no more than 5 DLTs are observed, the trial will proceed to the second-stage and enroll an additional 15 patients. Of note, more than 3 responses and fewer than 10 DLTs in the total study cohort will indicate statistically significant improvement in response and toxicity.

Thus, the total number of evaluable patients following the second-stage will be N=27, in order to have 93% power to detect an improvement in response rate from 10% based on prior literature in this patient population to 30% with novel combination treatment and a toxicity of less than 40%. The rationale to design the study to detect this rate of improvement was that 10 to 30% is felt by the investigators to represent a clinically meaningful increase in response rate. Given the sample size of 27, a two-sided 90% confidence interval for a single proportion of ORR will extend 0.145 from the observed proportion for an expected proportion of 0.30. Similarly, the confidence interval for toxicity will extend 0.127 from the observed proportion for an expected proportion of 0.20.

We anticipate enrollment of a maximum of 39 patients: this includes the 27 total evaluable patients at RP2D; correction for an unevaluable, i.e., dropout rate of 8-10% after monotherapy (3 patients); and the dose-finding requirement of up to 9 additional patients should dose adjustment be needed due to toxicity. Further details of the statistical methods and operating characteristics of this Bayesian monitoring are found in **Section 9.2**.

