3.1 END OF STUDY ENROLLMENT

In the first quarter of 2021, study supporters Aravive and AstraZeneca made the decision to end enrollment based on available data after the 5th evaluable subject completed treatment on the safety lead-in.

[figure not shown]

Figure 2. Study Schema

Dosing schedule as above demonstrates investigational product at week of administration, where A = AVB-S6-500 monotherapy, D= durvalumab monotherapy, and A+D = AVB-S6-500 + durvalumab combination therapy

* Patients receiving the recommended Phase 2 dose (RP2D) will then be included in the primary analysis of the combination therapy. However, these patients will continue on the Safety Lead-in dosing schedule and will not participate in the Phase 2 monotherapy. See de-escalation dosing regimens below.

† Sample size calculations account for predicted 8% dropout rate due to toxicity.

‡ Dosing schedule shown reflects the starting dose for the dose escalation. This may be adjusted for the de-escalation schedule below and determination of the RP2D.

Table 1. Dosing for Dose Escalation

Dose Level	Durvalumab + AVB-S6-500
Dose Level 0 (Initial dose)	durvalumab (1500mg Q4W), AVB-S6-500 (10mg/kg Q2W)
Dose level 1	durvalumab (1500mg Q4W), AVB-S6-500 (15mg/kg Q2W)
Dose level 2	durvalumab (1500mg Q4W), AVB-S6-500 (20mg/kg Q2W)

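### Section 9 prints dose-decision cut-offs of 0.236 and 0.359 beside a 25% DLT target; they contradict Table 12 in eight cells, always toward more exposure

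*Combined protocol and SAP*

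**What the plan says.** Section 9 opens the dose-finding design with "The target toxicity rate for the MTD is $\phi = 0.25$ and the maximum sample size is 18". Cohort size follows: "We will enroll and treat patients in cohorts of size 3". The next cohort goes up a level "if the observed DLT rate at the current dose is ≤ 0.236"; for de-escalation, "if it is ≥ 0.359 , the next cohort of patients will be treated at the next lower dose level". A dose is eliminated when the posterior probability that its DLT rate exceeds 0.25 is above 0.95.

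Step 2 then tells the site to "conduct dose escalation/de-escalation according to the rule displayed in" Table 12, which gives the same decisions as DLT counts for 1 to 12 patients. Under note 2d, patients stay at the lowest dose when the rule says de-escalate, unless the elimination boundary is reached. Step 3 stops at 15 patients, when "the maximum of 5 evaluable patients are treated on the highest dose", or when at least 9 patients have been treated at the current dose and Table 12 says stay.

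Table 13 gives operating characteristics for a target of 0.25. Section 3.1 reports that the supporting companies "made the decision to end enrollment based on available data after the 5th evaluable subject completed treatment on the safety lead-in".

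**The concern.** The same section gives two rules for one decision. Table 12 de-escalates at 1 DLT in 3 patients. One in three is 0.333, below 0.359, so the text keeps the next cohort where it is. Both are worded as instructions, and nothing says which prevails.

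Anyone who applies, audits or reports the dose finding from the sentence would use a rule that does not match the stated target, Table 12 or the simulations in Table 13. The primary objective in Section 2.1 is the toxicity profile of the combination, so the rule that governed exposure is part of what the report must describe.

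**Working it through.** **Inputs.** Target φ = 0.25, printed cut-offs 0.236 and 0.359, cohorts of 3, and Table 12, all from Section 9. The protocol does not give the BOIN alternatives, so I assume the defaults p1 = 0.6φ and p2 = 1.4φ.

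**Formulas.**
- Escalate at or below λe = ln[(1−p1)/(1−φ)] / ln[φ(1−p1)/(p1(1−φ))]
- De-escalate at or above λd = ln[(1−φ)/(1−p2)] / ln[p2(1−φ)/(φ(1−p2))]

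**Target 0.25** (p1 = 0.15, p2 = 0.35)
- λe = ln(0.85/0.75) / ln(0.2125/0.1125) = 0.1252/0.6360 = 0.1968
- λd = ln(0.75/0.65) / ln(0.2625/0.1625) = 0.1431/0.4796 = 0.2984

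**Target 0.30** (p1 = 0.18, p2 = 0.42)
- λe = ln(0.82/0.70) / ln(0.246/0.126) = 0.1582/0.6690 = 0.2365
- λd = ln(0.70/0.58) / ln(0.294/0.174) = 0.1881/0.5245 = 0.3585

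The printed pair is therefore the default for a 30% target.

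**What Table 12 requires.** It does not escalate at 1/5 but does at 2/11, so its escalation cut-off lies in [0.182, 0.200). It de-escalates at 3/10 but not at 2/7, so its de-escalation cut-off lies in (0.286, 0.300]. The pair 0.197 and 0.298 fits and reproduces both rows for n = 1 to 12. Both printed numbers fall outside. This step needs no assumption about the alternatives.

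**Elimination row.** A uniform prior with Pr(p > 0.25) > 0.95 reproduces it from n = 3. A limit of 0.30 would change it at n = 5, 7, 8, 10 and 12. The table was built for 0.25.

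**Conflicts, n = 1 to 12**

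| DLTs/patients | Rate | Text | Table 12 |
|---|---|---|---|
| 1/3, 2/6, 3/9, 4/12 | 0.333 | stay | de-escalate |
| 2/9 | 0.222 | escalate | stay |
| 1/5, 2/10 (partial cohorts) | 0.200 | escalate | stay |
| 3/10 (partial cohort) | 0.300 | stay | de-escalate |

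**Which rule produced Table 13.** Simulated with N = 15, no cap at the highest dose, 6,000 runs:

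| Scenario | Measure | Printed | 0.197/0.298 | 0.236/0.359 |
|---|---|---|---|---|
| 1 | Selection % by dose | 73.4/19.1/1.2 | 73.9/18.2/1.0 | 66.5/23.9/2.8 |
| 2 | Patients per dose | 6.7/5.0/2.4 | 6.7/5.2/2.4 | 5.0/6.0/3.5 |
| 3 | Selection % by dose | 6.0/40.0/54.0 | 6.2/39.0/54.7 | 3.5/31.0/65.5 |

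Table 13 follows the 0.25 rule.

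**Size, with the protocol's steps as written** (cohorts of 3, cap of 5 at the highest dose, 20,000 runs). The two text columns differ in whether the step 3 stop is read from Table 12, as step 3 says, or from the text.

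| Quantity | Table 12 rule | Text, stop by Table 12 | Text, stop by text |
|---|---|---|---|
| Scenario 2, N = 15: selects the 40%-DLT dose | 20.4% | 28.2% | 31.1% |
| Scenario 2, N = 15: mean patients on that dose | 2.05 | 2.45 | 2.69 |
| Scenario 1, N = 15: mean patients above the MTD | 3.14 + 0.53 = 3.67 | 4.00 + 0.66 = 4.66 | 4.43 + 0.74 = 5.17 |
| Scenario 2, N = 18: selects the 40%-DLT dose | 23.2% | 28.7% | 33.7% |

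Following Table 12 with N = 15, a 1/3 result at the middle or highest dose, where the two rules part, occurs in 29%, 55% and 55% of trials (Scenarios 1, 2 and 3).

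**The case against.** The strongest reply is that the protocol already shows which rule operates. Step 2 assigns doses by Table 12, its notes explain how to use that table, and step 3 bases stopping on it. The target, the elimination rule and Table 13 all agree with it. On that view the cut-offs are a stale pair of numbers in a preamble. This is a fair reading and probably the intended one. It limits the harm but leaves a directive sentence that says something else.

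Several of the eight cells also cannot change a dose if steps 1 to 3 are followed with N = 15:
- At 2/9, step 3 ends enrollment, so there is no next cohort.
- At 4/12, the total is already 15 at the middle dose, the highest dose is capped at 5, and note 2d holds patients at the lowest dose.
- 1/5, 2/10 and 3/10 need partial cohorts.

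That leaves 1/3, 2/6 and 3/9 at the middle dose and 1/3 at the highest. This stands, as does its corollary that the stop-by-Table-12 column is the better supported one.

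The size also depends on the setting. Without the cap, selection of the 40%-DLT dose in Scenario 2 goes from about 17% to 22%. In Scenario 3, where the highest dose is the true MTD, the text rule raises correct selection from about 60% to between 68% and 70%, as any more aggressive rule would. That does not make it the rule for a 25% target.

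Finally, enrollment is over, and Section 9.2.3 required IND Office approval before a dose change. If five is the lead-in total and the first cohort of 3 was treated at the lowest dose, the rules agree after that cohort: both escalate at 0/3, both keep patients at that dose at 1/3 and 2/3 (note 2d), and both eliminate at 3/3. If five refers instead to the highest-dose cap in step 3, earlier decisions could have differed. The documents do not settle this or show which rule was applied.

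**Conclusion.** The concern holds: the printed cut-offs are wrong for the stated target and contradict Table 12 in eight cells, each time in the less cautious direction. The contradiction is count arithmetic on the protocol's own numbers. Only the attribution to a 30% target rests on the assumed default alternatives.

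If the text were followed in place of Table 12, the best-supported cost under the written stopping rules is about 8 percentage points more selection of a 40%-DLT dose in Scenario 2 (20.4% to 28.2%) and about one more patient above the MTD in Scenario 1 (3.67 to 4.66).

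The remaining effect on patients is small, but the correction should still be made. The statement in Section 9 that the original design no longer applies covers the phase II text that follows it, not the dose-finding text above, so the wrong threshold sits in current wording.

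**What to change.** In Section 9, replace 0.236 with 0.197 and 0.359 with 0.298. Check that Figure 3, which could not be seen here, carries the same pair. Add one sentence saying that Table 12 governs if text and table differ. Tables 12 and 13 need no change on this account. In the study report, state which rule was applied to the patients already treated, with the dose and DLT count at each decision.

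The cost is two numbers and one sentence of protocol wording, plus a short statement in the report. No new patients or data are needed.

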6. TREATMENT PLAN

6.1 PROCEDURES FOR RANDOMIZATION

Subjects will be recruited from the Department of Gynecologic Oncology and Reproductive Medicine at The University of Texas MD Anderson Cancer Center. Patients with platinum resistant high grade ovarian, primary peritoneal, or fallopian tube cancers will be screened by the designated research staff and/or study investigators for eligibility. Interested patients will be approached and provided information regarding the study and potential eligibility and participation. After informed consent, screening evaluation will be performed to determine eligibility. Patients may elect to leave the study at any time.

We will enroll up to 30 evaluable subjects with platinum-resistant EOC at an expected rate of 3 subjects per month. Subjects will be evaluable for the primary objective once they have completed one cycle of combination therapy at the RP2D. Up to 12 evaluable subjects will be enrolled into the dose de-escalation combination phase (Safety Lead-in) to determine the RP2D. Once the RP2D is determined, subsequent subjects will be randomized to monotherapy arms as described below. To replace patients that are registered but do not proceed to treatment (e.g. screen failures), an additional 15 patients may be

registered; however, a maximum of 30 evaluable patients will be treated as per the protocol. Subjects will be treated until disease progression or until unacceptable toxicity. We will follow all patients for at least 12 months, and we will employ safety and efficacy monitoring rules as described in **Section 9.2.1** and **Section 9.2.2**.

Following RP2D determination, we will randomly assign patients to one of two monotherapy treatment arms (durvalumab or AVB-S6-500) at a ratio of 1 (durvalumab) to 3 (AVB-S6-500). All patients, with the exception of any who meet discontinuation criteria, will then receive combination treatment regimen.

Randomization will be carried out using CORe.

Subjects who are incorrectly enrolled but have not been initiated on treatment will be withdrawn from the study. Such subjects will be replaced. Any subjects who are incorrectly enrolled and randomized and initiated on therapy will be reported to the IRB as a protocol violation. Such subjects will be evaluated on an individual basis by the PI and the decision to continue treatment or withdraw will be based on an analysis of risk/benefit for the subject.

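### Table 13 describes a BOIN design with 15 patients and no 5-patient stop at the highest dose, not the rule in step 3; three different lead-in maxima stand in the live text, and Table 13 contradicts its own allocation sentence

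*Combined protocol and SAP*

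**What the plan says.** Section 9 opens the BOIN description with a target DLT rate of 0.25 "and the maximum sample size is 18". Step 3 of the same rule then continues "until the maximum of 5 evaluable patients are treated on the highest dose, or maximum sample size of 15 is reached", with a further stop once at least 9 patients have been treated at the current dose and the Table 12 decision is to stay. Section 6.1 gives a third maximum: "Up to 12 evaluable subjects will be enrolled into the dose de-escalation combination phase (Safety Lead-in) to determine the RP2D".

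The text above Table 13 says that "Table 13 shows the operating characteristics of the trial design based on 1000 simulations of the trial using the BOIN Design Desktop Program". It adds that the design "allocates more patients to the dose levels with the DLT rate closest to the target of 0.25".

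Section 3.1 records that the supporting companies "made the decision to end enrollment based on available data after the 5th evaluable subject completed treatment on the safety lead-in". Below Table 13, Section 9 says: "The trial will be completed after the RP2D is determined as described above". The note that follows retires only the text after it, so step 3, Table 13 and Section 6.1 all remain in force.

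**The concern.** In Scenario 3, Table 13 reports an average of 4.9 patients on the highest dose. If enrolment ends when that dose has 5 patients, an average so close to 5 would require almost every trial to reach and fill the top dose. That is implausible when the top dose has a true DLT rate of 25% and the maximum is 15.

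Dose finding is the part of the design that still applies, and Table 13 is the plan's only statement of how reliably it finds the MTD. If the table belongs to a different stopping rule, any recommended phase 2 dose will be read against the wrong selection probabilities, including the chance of picking a dose that is too toxic. Three different maxima also leave open which design was simulated.

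**Working it through.** **Inputs.** From Section 9: target 0.25, cohorts of 3, start at dose 1, the Table 12 boundaries, elimination with a stop if the lowest dose is eliminated, isotonic MTD selection, and the three scenarios of Table 13. Eliminated doses are excluded from selection. All trial paths were enumerated exactly. Ranges cover two readings of the stop at 9 patients: stop only if the next cohort would stay at the same dose, or stop at 9 whatever the decision.

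**Patients treated (maximum 15).** With the 5-patient stop, the second top-dose cohort is cut to 2.

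| Scenario | Version | Dose 1 | Dose 2 | Dose 3 | Total |
|---|---|---|---|---|---|
| 1 | Table 13 | 8.2 | 3.0 | 0.6 | 11.75 |
| 1 | No 5-patient stop | 8.22 | 2.95–3.11 | 0.58 | 11.75–11.92 |
| 1 | With stop | 8.22 | 2.94–3.10 | 0.53 | 11.69–11.85 |
| 2 | Table 13 | 6.7 | 5.0 | 2.4 | 14.08 |
| 2 | No 5-patient stop | 6.66 | 4.93–5.15 | 2.46 | 14.05–14.27 |
| 2 | With stop | 6.66 | 4.86–5.08 | 2.06 | 13.58–13.80 |
| 3 | Table 13 | 4.8 | 5.1 | 4.9 | 14.75 |
| 3 | No 5-patient stop | 4.81 | 5.02–5.12 | 4.89 | 14.72–14.81 |
| 3 | With stop | 4.81 | 4.91–5.00 | 3.67 | 13.38–13.48 |

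The version without the stop reproduces Table 13; the version with it does not. In a separate Monte Carlo check, the Scenario 3 gaps between Table 13 and the rule with the stop were about 21 standard errors of a 1000-trial run for the top-dose count and 23 to 25 for the total.

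**A bound that needs little simulation.** With the stop, the top-dose count can only be 0, 3 or 5. If a fraction x of trials does not fill the top dose, the mean is at most 5 − 2x. Setting 5 − 2x = 4.9 gives x = 0.05, so at least 95% of trials must fill it. If 4.9 is a rounded 4.85, the figure is 92.5%. By enumeration, 59.5% do.

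**Selection (%).**

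| Scenario | Quantity | Table 13 | No stop | With stop |
|---|---|---|---|---|
| 1 | Correct dose | 73.4 | 73–74 | 73–74 |
| 1 | Top dose (59% DLT) | 1.2 | 1.1 | 1.8 |
| 2 | Correct dose | 56.6 | 53.1 | 49.1 |
| 2 | Top dose (40% DLT) | 14.5 | 16.4 | 20.4 |
| 3 | Correct dose | 54.0 | 55.0 | 59.8 |

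In Scenario 2 the gap in correct selection is 56.6 − 49.1 = 7.5 points. The stop accounts for 53.1 − 49.1 = 4.0. The other 56.6 − 53.1 = 3.5 points compare with a Monte Carlo standard error of √(0.531 × 0.469 / 1000) = 1.58 points, a ratio of 2.2.

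**Which maximum fits.** Without the 5-patient stop, a maximum of 12 gives totals of 10.62, 11.71 and 11.92; it cannot average 14.08 or 14.75. A maximum of 18 gives 12.15–12.83, 15.40–16.56 and 16.54–17.10. With the stop, 18 gives about 3.9 top-dose patients in Scenario 3, against 4.9 stated. Only 15 without the stop agrees.

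**A looser reading of the stop.** If the second top-dose cohort is completed, so that 6 are treated, Scenario 3 has 4.3 top-dose patients, a total of 14.0–14.1 and 56.1% correct selection. The patient counts still differ from Table 13.

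**Allocation sentence, from Table 13 alone.** Scenario 1: 8.2 of 11.75 patients are on the 25% dose, so it holds. Scenario 2: 6.7 on the 10% dose against 5.0 on the 25% dose, so it fails. Scenario 3: 5.1 on the 12% dose against 4.9 on the 25% dose, nearly equal and no support. Under step 3 as written, the 25% dose in Scenario 3 receives the fewest patients of the three (3.67).

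**The case against.** The strongest objection is about weight. Enrolment closed after the fifth evaluable lead-in subject, Table 13 feeds no analysis in Section 9.2, and the recommended dose may be adjusted on PK/PD and the total evidence. The 5-patient stop may be close-out text added after the simulation, since its number matches Section 3.1. The table would then be a sound simulation of an earlier rule. This is plausible but an inference, and it would explain the mismatch without curing it: the current text attributes those figures to the current design.

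A second objection is that step 3 does not define a unique design. Section 9 also quotes escalation and de-escalation cut-offs of 0.236 and 0.359, which conflict with Table 12: with 1 DLT in 3 patients, the text says stay and Table 12 says de-escalate. Under the text cut-offs with the 5-patient stop, Scenario 3 correct selection would be about 72%, and the 40% DLT dose in Scenario 2 would be chosen about 31% of the time. The 25% dose in Scenario 3 would then no longer receive the fewest patients. This conflict is real and separate. Step 2 makes Table 12 the operative rule, and Table 13 follows Table 12, so the comparison above stands.

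Two smaller points are fair. The maximum of 12 in Section 6.1 looks like a remnant of an earlier de-escalation design. The allocation sentence names no comparator, and the starting dose always receives the first cohort; even so, Scenario 2 does not bear the sentence out.

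**Conclusion.** The concern holds and should be fixed. Table 13 does not give the operating characteristics of the rule in step 3. The patient counts in Scenario 3 settle this under either reading of the stop at 9 patients and under the looser reading of the 5-patient stop.

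The effect of the stop is mixed. The top dose is selected more often whether it is the right dose (Scenario 3, stated 54.0%, about 60% under the rule) or too toxic (Scenario 2, stated 14.5%, about 20%). Scenario 2 correct selection is about 49% against 56.6% stated, with part of that gap attributable to simulation error. Scenario 1 correct selection is unchanged.

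These figures assume the Table 12 boundaries, cohorts of 3 and a top-dose cohort cut to reach 5. The conflict among 18, 15 and 12, and the Scenario 2 contradiction of the allocation sentence, can be read directly from the document.

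**What to change.** 1. State one lead-in maximum, 15, in Section 6.1 and at the start of Section 9, to agree with step 3 and Table 13.
2. Re-run Table 13 with the 5-patient stop and report those figures, or label the current table as a maximum of 15 without that stop. Either way, state that the Table 12 boundaries were used and how the stop at 9 patients was applied. The Scenario 2 total of 14.08 lies closer to stopping at 9 on any decision (14.05) than to stopping only on a stay decision (14.27).
3. Delete the allocation sentence, or restrict it to Scenario 1.

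The cost is one re-run or a footnote, plus edits to three sentences. No patients are added, and no dosing or enrolment decision changes.
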